The Primary Aim of Study 2 is to compare the effects of cigarettes varying in nicotine yield on smoking rate. The primary endpoint is cigarettes per day (CPD) at 12 weeks. CPD will be collected by daily IVR and/or TLFB at each session to assess cigarette use in the days since the last interview. This will yield a continuous record of cigarette use throughout the study. A weekly average will be obtained for analysis by averaging CPD from the previous visit to the current visit. Additional measures addressing this aim are breath CO level, urinary cotinine concentration, and nicotine dependence (FTND, WISDM) scores. Secondary Aim 1 is to assess adherence to assigned tobacco products and use of multiple nicotine

products during extended exposure. Secondary Aim 2 is to quantify the effects of VLNC cigarettes on (a) biomarkers of exposure to tobacco carcinogens (urine total cotinine, NNAL, PAH)s.

To examine these Aims, repeated measures analysis of variance (ANOVA) will be used for outcomes that are measured repeatedly from baseline to the end of the treatment phase. Each repeated measures ANOVA model consists of five terms: cigarette condition effect, visit effect, interaction effect between cigarette condition and visit, random subject effect (between-subject error), and random error (within-subject error). The variance-covariance structure will be specified as the first-order autoregressive, and variance parameters will be estimated using restricted maximum likelihood method with the Satterthwaite approximation. First, the VLNC condition will be compared to the usual brand condition; if significant differences are observed ($p < 0.05$), the simple effects of visit will be examined within the VLNC condition and the usual brand condition. Biomarkers will be analyzed on natural log scales so that ANOVA model assumptions of normality and equal variances hold. Geometric means in original units will be calculated as well. Interaction terms between BMI and cigarette condition will be added to these models to explore possible moderating effects of obesity on the relationship between cigarette condition and biomarkers. Differences between groups in self-reported quit and cigarette reduction rates at the 4-week post-treatment follow-up period will be evaluated using Chi-square tests, as will be the case for other discrete outcomes such as drop-out rates. SAS (SAS Institute Inc., USA) will be used for most analyses, but may be supplemented by use of STATA or R.

Sample size. Sample size for other analyses was determined using power analysis for hypothesis tests related to the Primary Aim of Study 2, specifically to detect a significant difference between the reduced-nicotine condition and the usual brand condition in the primary endpoints, cigarettes per day (CPD) and urine cotinine, at the end of the trial. Effect size estimates were based on our previous studies of normal nicotine cigarettes (NNC) and VLNC use in disadvantaged women of childbearing age and estimates of CPD in our completed study on smoking topography in pregnant women and women of childbearing age. In that study, pregnant women smoked an average of 12.1 CPD, while preliminary data from our trial of women of childbearing age suggest a decrease of 5 CPD in women smoking VLNC compared to those smoking NNC. A sample size of 45 completers per condition will provide 80% power to detect statistically significant differences in smoking rate.

Potential Risks of Participation

- 1) Smoking Cigarettes: All cigarettes are detrimental to a person's health and can lead to significant medical problems including:
 - a. Risk to Fetus: Miscarriage, preterm delivery, stillbirth, low birth weight, problems with the placenta, birth defects such as cleft palate, sudden infant death syndrome (SIDS), and early childhood behavioral problems.
 - b. Cardiovascular Diseases: Coronary heart disease, heart attack, stroke, peripheral vascular disease, reduced blood circulation, abdominal aortic aneurysm
 - c. Respiratory Diseases: Emphysema, bronchitis, and chronic airway obstruction
 - d. Cancers: Cancer of the lung, bladder, cervix, esophagus, kidney, larynx, mouth, pancreas, throat, and stomach; leukemia
 - e. Metabolic Diseases: Type 2 Diabetes

- f. Other Health Risks Associated with Smoking: Including but not limited to infertility, lower bone density in postmenopausal women, and hip fracture in women
 - g. Death
- 2) Smoking Withdrawal: Participants may experience smoking withdrawal symptoms during this study. The symptoms can be uncomfortable but are typically of minimal risk. Smoking withdrawal symptoms include:
 - a. Anger, irritability, frustration
 - b. Anxiousness, nervousness
 - c. Depressed mood or sadness
 - d. Desire or craving to smoke
 - e. Difficulty concentrating
 - f. Increased appetite, hunger or weight gain
 - g. Insomnia, problems sleeping or awakening at night
 - h. Restlessness
 - i. Impatience
 - j. Constipation
 - k. Dizziness
 - l. Coughing
 - m. Dreaming or nightmares
 - n. Nausea
 - o. Sore Throat
- 3) Sample Collection: Breath samples to measure cigarette use and urine tests to confirm pregnancy will be carried out. The results of these tests may be upsetting to participants or cause them discomfort.
- 4) Survey Questionnaires: The interview will include questions about medical and psychiatric history and questionnaires about mood. Answering these personal questions could make the participants feel uncomfortable. Participants can choose not to answer any questions that make them uncomfortable. If a participant reports thoughts of killing themselves or other indicators of suicidality, a study clinician will speak with them. They may also request to talk with a study clinician if they are in discomfort and would like help and/or referrals for mental health resources.
- 5) Exacerbation of psychiatric symptoms: Smoking and nicotine can affect a person's mood and emotions and are associated with psychiatric disorders including major depressive disorder, general anxiety disorder, bipolar disorder and eating disorders. Any changes in nicotine or cigarette consumption could adversely affect psychiatric conditions.
- 6) Obtaining blood pressure: The blood pressure cuff may cause minimal discomfort. In obtaining blood pressure, researchers may find the participant has abnormal blood pressure. If a participant's blood pressure is abnormal, we will inform them of this and may advise them to see a doctor. Our licensed medical professional may also contact them.
- 7) Changes in blood pressure and/or heart rate: Smoking and nicotine can affect the cardiovascular system which may result in changes in blood pressure and/or heart rate.
- 8) Breach of Confidentiality: The risk of the interview is loss of privacy if other people find out the results.

9) Undue Influence: Undue influence is a possible risk due to monetary compensation for participating in the study. The likelihood of this risk is low because the compensation is commensurate with the amount of time and effort required for these studies.

Expected benefits of participation:

There are no immediate benefits from participating in the study. The information obtained from this study may ultimately help the Food and Drug Administration decide how best to regulate tobacco products with the goal of improving public health.

Protection Against Risk

Research data without identifiers will be maintained in a locked file cabinet and on password-protected computers in the research staff workplace, with only code numbers identifying subjects. Study consent forms and the linkage between the participants' names and codes will be stored in a locked file cabinet. Interviews with participants will be conducted in private rooms. Urine samples for pregnancy tests and tobacco exposure biomarkers will be obtained in a private bathroom within the laboratory suite. Subjective measures will be administered electronically. The biostatistics and data-management team will provide consistent data-management practices for all data in the Center. Validity and reliability of data will be maximized by using REDCap which, is a secure, web-based system that accommodates local and remote data collection by the project team, and allows for data entry work-flow monitoring and data quality control monitoring by biometry staff. For data integrity, data entry windows will follow the structure of paper forms as much as possible to allow for ease of entry, and will use predefined choices to minimize errors when possible. Data quality monitoring will be facilitated with periodic down loads and analysis using a variety of common statistical program format such as SAS, Stata, R, and SPSS. Quality control procedures will be conducted for all data collected, including analysis of missing data and logic checks for out of range and other anomalous values. This secure electronic data gathering and transmission plan, overseen by the experienced biostatistical team, will minimize opportunities for breaches of confidentiality. Biological samples for nicotine and carcinogen biomarker analysis will be marked with participant ID, stored in the locked laboratory suite, and sent to a laboratory for analysis on a quarterly basis.

All information collected as part of this study will be accessible only to research staff. No information will be shared with participants' clinicians unless the participant requests this in writing. All investigators and staff have undergone (and any new staff will undergo) human subjects' ethics training as required by UVM and are fully conversant with relevant ethical principals around confidentiality. Assessments, consenting and study procedures will be closely supervised by the PI.

The sponsors (NIDA/FDA) as well as the Institutional Review Board and regulatory authorities could be granted direct access to original medical and research records for verification of clinical trial procedures and/or data. If this is required, it will be done under conditions that will protect privacy to the fullest extent possible consistent with laws relating to public disclosure of information and the law-enforcement responsibilities of the agency.

Data Storage:

Data will be stored locally for at least 7 years after study completion at the University of Vermont.

Adverse Events

The research assistant will ask about adverse events at each visit during the study, using a form that assesses the nature, severity, duration, action taken, and outcome of study-related adverse events. AEs will be captured from the time of study consent. Participants will be given contact cards to inform us of events that occur between study contacts. Any AE that remains open will be reviewed and closed at the study completion date (completers, withdrawn, etc.)

All procedures will be monitored to ensure that they conform to the approved protocol. In addition, monitoring will be done of all unforeseen circumstances that might arise and affect safety; of all reports of serious adverse events as defined in 38 CFR 46 (death, new or prolonged hospitalization, persistent or significant disability/incapacity); of other significant adverse events (adverse events that lead to drop out by the participant or termination by the investigator); of unexpected adverse events resulting from the study, and of expected adverse events.

Any SAE will be brought to the attention of the site PIs as soon as possible and not longer than 24 hours. Any AE or SAE that is both unexpected and related to study participation will be reported to the IRB within 7 days of the event. The IRB will make a determination as to whether additional reporting requirements are needed. IRB actions will be reported to the funding agency by the PIs no less than annually and more frequently as recommended by the local IRB. Any SAEs will be summarized in the yearly Progress Reports to the funding agency, including a review of frequency and severity. All SAEs will be followed through ongoing consultation with the physician caring for the patient until they resolve, result in death, or stabilize and are not expected to improve. The study staff will be in close contact with participants and health care providers throughout the study to monitor for potential unanticipated problems. Any unanticipated problems will be discussed at the weekly research staff meetings and reported as required to the local IRB.

Withdrawal or Monitoring of Participants

For the participant's protection, participants will be withdrawn immediately from the study if any of the following occur:

- 1) Pregnancy complication: Typically includes miscarriage, stillbirth, or preterm delivery.
- 2) Cardiovascular disease (CVD) event: Typically includes MI (heart attack), PTCA (angioplasty/stenting), bypass surgery, stroke, peripheral vascular disease (arterial blockages in arms or legs leading to procedure or surgery). Less common CVD problems would be new cardiac arrhythmias (e.g., new atrial fibrillation) or new valvular disease (e.g., mitral or aortic regurgitation).
- 3) Deep vein thrombosis (DVT)/pulmonary embolism (PE): I.e., blood clots in the venous system.
- 4) Suicide attempt: A participant will be withdrawn if she attempts suicide at any time during participation in the study.
- 5) Psychiatric hospitalization: A participant will be withdrawn if she is hospitalized for psychiatric reasons at any time during participation in the study.

- 6) Expired breath CO increase: A participant will be withdrawn from the study if the average of two consecutive CO readings during the same visit is more than double their Baseline exhaled CO measurement, or greater than 50 ppm at any given time.

The following will be monitored and can lead to the participant being withdrawn by the PI or Licensed Medical Professional:

- 1) BP or HR changes: If any of the following occur after informed consent: 1) BP is at or above 140/90 or below 80/50, or 2) HR is at or above 110 bpm or below 45 bpm a manual blood pressure and heart rate measurement will be taken after 10 minutes have passed. If the manual reading is still out of range, a 'Blood Pressure and Heart Rate Symptom Checklist' and 'Medical Event Form' will be completed, and the participant will be monitored by the medical professional.
- 2) Any hospitalization or debilitation in which participation in the study could be detrimental to the recovery process. This will be self-reported by the participant and will be reviewed by the site PI and medical professional to determine whether continued participation in the study is appropriate.
- 3) If a participant is behaving in an inappropriate or threatening manner, admits to lying about eligibility criteria, is participating in other smoking research studies that could affect the primary outcome measures, etc., then the PI can withdraw her from the study at the PI's discretion.
- 4) If a participant fails to attend regularly scheduled research assessment visits or comply with the research procedures or schedule, then the PI can withdraw her from the study at the PI's discretion.

Data Safety Monitoring Board

A Data and Safety Monitoring Board (DSMB) has been established to monitor safety outcomes and will be comprised of five members. The DSMB will be chaired by [name], Ph.D., M.P.H., Associate Professor of Preventive Medicine and Public Health at the University of Kansas and Director of the University of Kansas Hospital's tobacco treatment program. Other members include: [name]., Professor in Residence of Biostatistics in Psychiatry at the University of California San Francisco and Director of the Quantitative Core of the San Francisco Treatment Research Center; [name], Associate Professor of Psychiatry at Harvard Medical School and Director of the Center for Addiction Medicine at Massachusetts General Hospital; [name]., Professor of Obstetrics and Gynecology and Director of UNC Horizons at University of North Carolina Chapel Hill; [name]., Research Leader, Baltimore Operation, Centers for Public Health Research and Evaluation, Battelle; [name]., M.P.H., Associate Professor of Preventive Medicine and Public Health at the University of Kansas and Director of the University of Kansas Hospital's tobacco treatment program.

Conflict of interest

The Board will be convened to serve both studies. None of the members will be otherwise affiliated with the center and each member will complete a conflict of interest disclosure form prior to each meeting. Ad hoc specialists may be invited to participate as non-voting members at any time if additional expertise is desired.

Monitoring activities and frequency of meetings

The DSMB will set their own agenda and decisions about monitoring; e.g. how frequently to monitor, what threshold requires changes to protocol or stopping the study, and whether to view raw or analyzed data. The DSMB will be given FDA and EMEA guidelines for DSMBs and recent reviews on DSMBs. A brief

report will be generated from each meeting for the study record and forwarded to each of the study site's Institutional Review Boards (IRB) and NIDA's Program Officer with the progress report. The DSMB will be available to convene outside of the regular meetings, if necessary. If concerns should arise regarding a particular subject, or any troublesome trends in the experiences of participants, they will make appropriate recommendations for changes in protocol, as needed. The project investigators will continue to examine safety data, blind to study condition, in case they wish to make study modifications. Before modifications are made, they will inform the DSMB and request their comments.

Communication plan to IRB, NIDA, and FDA (if applicable)

All IRBs, the FDA and the NIDA's Program Officer will be informed of any significant action taken as a result of the Data and Monitoring Board's findings. Study Participants will be informed of any changes in risk.

Protection of confidentiality

For DSMB meetings only de-identified data, including blinded study site and condition type, will be provided to the board. All data and discussion during the meeting will be confidential.

Investigational Tobacco Product

The Vermont Center on Tobacco and Regulatory Science has received an Investigational Tobacco Product (ITP) application from the FDA to cover the experimental cigarettes being used in this study. This application encompasses both Project 4 sites.

Certificate of Confidentiality

To help protect the participant's privacy, [name], PhD, has received a Certificate of Confidentiality from the National Institutes of Health. With this certificate, the researchers cannot be forced to disclose information that may identify the participants, even by a court subpoena, in any federal, state, or local civil, criminal, administrative, legislative, or other proceedings. The researchers will use the Certificate to resist any demands for information that would identify the participants, except as explained below. The Certificate cannot be used to resist a demand for information from personnel of the United States Government that is used for auditing or evaluation of federally funded projects or for information that must be disclosed in order to meet the requirements of the Federal Food and Drug Administration (FDA).

The Certificate of Confidentiality does not prevent the participant or a member of their family from voluntarily releasing information about themselves and their involvement in the research. If an insurer, employer or other person obtains the participant's written consent to receive research information, then the researcher may not use the Certificate to withhold that information.

The Certificate of Confidentiality does not prevent the researchers from disclosing voluntarily, without consent, information that would identify the individual as a participant of the research project in instances such as evidence of child abuse or a participant's threatened violence to self or others.

Outcome Variables

Primary Endpoints for Study 1:

- 1) Nicotine withdrawal (i.e., MNWS)
- 2) Rank ordering of ability of each nicotine cigarette dose to substitute for usual brand dose cigarette

3) Establish cross-price elasticity for each nicotine dose

Primary Endpoints for Study 2:

- d. Number of cigarettes smoked per day: study cigarettes, combined study and non-study cigarettes
- e. Measure of exposure (i.e., urinary cotinine, expired breath CO, nicotine dependence)

Secondary Endpoints for Studies 1 and 2:

- 1) Measures of adherence: non-study cigarette use, drop-out rate
- 2) Measures of psychiatric symptoms: BDI, OASIS
- 3) Measures of discomfort/dysfunction: MNWS, QSU-brief
- 4) Measures of other health-related behaviors: weight (Study 1 only)
- 5) Measures of nicotine/tobacco dependence: FTND, WISDM-brief
- 6) Measures of tobacco exposure: CO, total nicotine equivalents, NNN, NNAL, minor alkaloids
- 7) Measures of intention to quit: Stages of Change, Contemplation Ladder
- 8) Measures of compensatory smoking: puff topography, filter analysis (Study 1 only)
- 9) Measures of other tobacco use: TLFB-other tobacco
- 10) Measures of cigarette characteristics: CES, CPT
- 11) Measures of cognitive function: BRIEF-A, EQ-5D, TPQ, D-KEFS, WASI-II, DDT, SST (Study 1 only)
- 12) Measures of cardiovascular function: heart rate, blood pressure, urine 11-dehydroTXB2
- 13) Measures of perceived risk: Perceived Health Risk Questionnaire
- 14) Safety outcome variables: Adverse Events (AEs), Serious Adverse Events (SAEs)

References

Alessi, S. M., Badger, G. J., & Higgins, S. T. (2004). An experimental examination of the initial weeks of abstinence in cigarette smokers. *Experimental and Clinical Psychopharmacology*, 12, 276-287.

Alsop, D. C., & Detre, J. A. (1996). Reduced transit-time sensitivity in noninvasive magnetic resonance imaging of human cerebral blood flow. *Journal of Cerebral Blood Flow and Metabolism*, 16, 1236-1249.

Ananth, C. V., Smulian, J. C., & Vintzileos, A. M. (1999). Incidence of placental abruption in relation to cigarette smoking and hypertensive disorders during pregnancy: A meta-analysis of observational studies. *Obstetrics & Gynecology*, 93, 622-628.

Army Individual Test Battery. (1944). *Manual of Directions and Scoring*. Washington, DC: War Department, Adjutant General's Office.

Bakketeig, L. S., Jacobsen, G., Hoffman, H. F., Lindmark, G., Bergsjø, P., Molne, K., & Rødsten, J. (1993). Pre-pregnancy risk factors of small-for-gestational age births among parous women in Scandinavia. *Acta Obstetrica et Gynecologica Scandinavica*, 72, 273-279.

Beck, A. T., Steer, R. A., & Carbin, M. G. (1988). Psychometric properties of the Beck Depression Inventory: Twenty-five years of evaluation. *Clinical Psychology Review*, 8, 77-100.

Beck, A. T., Ward, C., & Mendelson, M. (1961). Beck depression inventory (BDI). *Archives of General Psychiatry*, 4, 561-571.

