The University of Vermont will be responsible for assigning product based on the randomization schedule being provided by the UVM Biostatistics Core, and shipping the study cigarettes to each site as needed based on recruitment. Usual brand cigarettes will be purchased by each site as needed. Each site will be responsible for tracking product received and distributed to participants, collecting unused product from participants, and returning unused VLNC cigarettes to UVM.

During weeks 1-12, participants will be provided with a 10-day supply of research cigarettes equivalent to 100% of their smoking rate. This will ensure adequate availability of cigarettes in the numerous locations participants may typically keep a supply (home, work, vehicle, etc.) as well as avoid expending the entire supply if they miss a scheduled visit. Participants will be instructed to use the research cigarettes through Week 12, at which point they are to discontinue product use.

If there is prior knowledge a participant will be missing a visit (i.e. planned vacation, laboratory closure, etc.), then the participant will be provided with an adequate supply of cigarettes to make up for the missed visit(s).

Participants will be asked to refrain from use of other non-study cigarettes during the study period. However, they will be told there is not a penalty for use of non-study cigarettes, and that it is crucial for them to report any use of non-study cigarettes or other nicotine or tobacco products. Throughout the baseline and experimental periods, an Interactive Voice Response (IVR) system will be used on a daily basis to record the number of study cigarettes and non-study cigarettes used the previous day. During the baseline and first experimental week, participants will also answer daily IVR questions about their mood. Participants will be seen weekly for assessments. Brief standardized review sessions focusing on compliance with the study cigarettes and other study procedures will be provided at each visit.

Product Accountability:

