### **8.1. Adverse Events**

Safety data will include the number of adverse events, classified as to category. Categories of events are based on the Medical Dictionary for Regulatory Activities (MedDRA). In addition to the type of event, adverse events will be categorized by severity, whether the adverse event is related to the study products/procedures, and whether the adverse event is expected.

Summary frequencies will be provided based on the overall number of events as well as separately by dose condition. In addition to the number of events of a particular type recorded, the percent of adverse events will be computed with the denominator being the number of participants in the safety population. Thus, the description of events will be reported as events/person. Categorization of the severity of events, relationship to study product/procedures, and expected nature of the event will be also reported as the frequency and percent of participants.

Safety analyses will be reported only to the DSMB and the appropriate Institutional Review Boards, with the exception that any serious adverse event will also be reported to the study sponsor.

Birth outcomes will be reported descriptively.

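### The protocol words the AE form as covering study-related events only, which conflicts with the SAP's tabulation of all AEs by relatedness and leaves room for non-serious AEs to be recorded differently by condition

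*Protocol*

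**What the plan says.** The protocol's Adverse Events section opens with a broad question: "The research assistant will ask about adverse events at each visit during the study". The same sentence then describes the instrument more narrowly: "using a form that assesses the nature, severity, duration, action taken, and outcome of study-related adverse events". Neither relatedness nor expectedness is among the fields named. The next sentence is broad again: "AEs will be captured from the time of study consent". The section also provides for monitoring "of all reports of serious adverse events as defined in 38 CFR 46".

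The visit lists under Study 2 Experimental Procedures include a Health Changes Questionnaire at every weekly visit and a Medical Event Form where applicable. Neither carries a relatedness condition.

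SAP 8.1 codes AEs by MedDRA category and then by severity, expectedness and "whether the adverse event is related to the study products/procedures". Frequencies are given overall and by condition, with the safety population as denominator. SAP 8 limits reported safety data to AEs and birth outcomes.

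On who knows the condition, Study 2 Randomization says "Usual brand cigarettes will be purchased by each site as needed". Study 2 Baseline Procedures and Study 2 Experimental Procedures have staff process returned product and dispense new product weekly.

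**The concern.** A table that splits AEs into related and unrelated needs both kinds to have been recorded. A form confined to study-related events settles that question at entry: an event judged unrelated never reaches the database, and the SAP's unrelated category is empty or arbitrary.

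The order of the two steps matters more in Study 2 than in a masked trial. If relatedness is judged before recording, the person judging may know whether the woman is smoking research cigarettes or the brand she smoked before enrolling. The protocol lists nausea among the withdrawal symptoms participants may have (Potential Risks of Participation) and also measures nausea as a pregnancy symptom (PUQE-24). The same complaint could be attributed to the study in one condition and to pregnancy in the other. The documents do not say whether usual brand counts as a study product when relatedness is judged.

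At stake are the by-condition counts of non-serious AEs, which SAP 8.1 sends to the DSMB and the IRBs. Masked review at a later stage cannot restore an event that was never logged.

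**Working it through.** The plan gives no AE rate, relatedness proportion or capture rate, so there is no figure to reproduce. The check is a side-by-side reading.

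**1. Is there a conflict?**

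| Item | Protocol, Adverse Events | SAP 8.1 |
|---|---|---|
| Events covered by the form | Study-related AEs | AEs, with no restriction |
| Relatedness | A condition of entry; not a listed field | A classification made on each AE |
| Expectedness | Not a listed field | A classification made on each AE |

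The two cannot both be followed as written. The qualifier is also not quite isolated: in the next paragraph of the protocol, the item on unexpected AEs is confined to those resulting from the study.

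**2. Does other text settle it?** Some of it points to full capture:

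- The visit question is about AEs generally.
- Capture starts at consent, whereas product is first given at Baseline 2, at least 7 days after Baseline 1. That fits poorly with a screen on product causality, although it is compatible with a screen on study procedures.
- Relatedness is an explicit filter for expedited reporting: "Any AE or SAE that is both unexpected and related to study participation will be reported to the IRB within 7 days". That condition would be redundant if only related events were ever recorded.

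None of this states a recording rule. No passage says that answers on the Health Changes Questionnaire become AE records. For the Medical Event Form, the only stated triggers concern blood pressure and heart rate. Because SAP 8 reports only AEs and birth outcomes, a health change that is never logged as an AE drops out of safety reporting. Two sites could read the section in two ways.

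**3. Could recording differ by condition?** Study 1 Randomization describes blind pack codes and says participants, investigators and staff will not know the product. Study 2 Randomization has no such statement, and sites buy the comparator. Participants and dispensing staff will therefore know the condition.

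Let c_V and c_U be the proportions of true AEs that get recorded on VLNC and on usual brand. Then

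observed rate ratio = true rate ratio × (c_V / c_U).

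If c_V = c_U the factor is 1: counts fall in both arms and the ratio is undisturbed. If they differ, the ratio is distorted by exactly that factor. The documents give neither quantity and set no different rule by arm, so the factor's size and direction are both undetermined.

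**4. Which safety data are exposed?**

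- SAEs: all reports are monitored, with no relatedness filter.
- Birth outcomes: taken from maternal medical records (Birth Outcomes Data).
- Blood pressure and heart rate: a confirmed out-of-range reading leads to a Medical Event Form in either arm (Withdrawal or Monitoring of Participants).
- Mood and nausea: BDI, OASIS and PUQE-24 are completed at every weekly visit regardless of cause, although this is outside AE reporting.
- Other non-serious AEs: these depend on the form, so this is where the conflict bites.

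**The case against.** The strongest reply is that 'study-related' is loose wording. The same section asks about AEs without restriction, captures them from consent and monitors all SAE reports. No passage describes a causality judgement before recording; that step is inferred from one adjective. Much of what might go missing is measured anyway by scheduled instruments in both arms. SAP 8.1 is descriptive, with no test, interval or model for AEs. All of this stands, and it limits the point to a wording conflict with a bounded consequence. It does not remove the conflict, because the scheduled instruments are not said to feed the AE record.

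Three stronger readings are tempting, and the documents do not support them.

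- A reader might infer that only related events are captured. The general question and the start at consent contradict so flat a statement.
- A reader might infer that usual-brand events will be under-recorded and the comparison biased towards apparent VLNC harm. No rule differs by arm, the protocol's risk list treats all cigarettes as harmful, and the expedited-reporting criterion refers to study participation rather than to the VLNC product. Neither direction nor size follows.
- A reader might take "The project investigators will continue to examine safety data, blind to study condition" (Monitoring activities and frequency of meetings) to be an error in an open-label study. Condition can be masked in a data review even when dispensing staff know it, and the board itself is to receive condition type in blinded form. That statement need not be reversed.

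**Conclusion.** The conflict is real and should be resolved. As worded, the form cannot supply the SAP's unrelated category, lists no field for two of the SAP's classifications, and allows a causality screen ahead of recording by people who know the condition. The consequence is an avoidable risk of differential recording, not a demonstrated bias, and its size and direction cannot be derived from the documents. It is confined to descriptive by-condition counts of non-serious AEs.

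This rests on two assumptions: that the form is used as the protocol describes it, and that research and usual-brand cigarettes are distinguishable to participants and dispensing staff. If sites already log every event regardless of cause, the defect is one of wording only, and the same amendment removes it.

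**What to change.** In the protocol's Adverse Events section:

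- Delete 'study-related' from the description of the form.
- State that every AE from consent onward is recorded regardless of presumed cause, and that answers on the existing Health Changes Questionnaire feed the AE record.
- Add relatedness and expectedness as form fields, judged after the event has been recorded.

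In SAP 8.1, state that the by-condition summary is based on all AEs, with related AEs shown as a subset.

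The cost is one deleted word, a few sentences, two form fields and somewhat more events to log, drawn from a questionnaire already given at each weekly visit.
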